#### Study centre and number of subjects planned

This study will be conducted at 1 study centre. Up to 36 healthy volunteers will be randomised to ensure evaluable data from at least 30 volunteers.

Study period	Phase of development
Estimated date of first volunteer enrolled	Phase I
Estimated date of last volunteer completed	

#### Objectives

#### **Primary objective**

To evaluate the bioavailability of the crushed ticagrelor tablets when administered orally or through nasogastric tubes, compared to whole ticagrelor tablets given orally by assessment of the area under the plasma concentration-time curve and maximum plasma concentration for both ticagrelor and AR-C124910XX, the active metabolite of ticagrelor.

#### Secondary objective

To examine the safety and tolerability of ticagrelor when administrated as dispersed tablets orally, dispersed tablets via nasogastric tube and as whole tablet orally by assessment of adverse events, safety laboratory variables, physical examination, electrocardiogram and vital signs.

#### Study design

This study is a single-centre, open-label, randomised, 3-period, 3-treatment crossover study in which healthy volunteers will receive single doses of ticagrelor in three different ways (treatment A, B, and C). A total of 36 healthy volunteers (male and female) will be randomised in this study to ensure that at least 30 volunteers are evaluable. The dose will be administrated as:

- Treatment A = Ticagrelor 90 mg (whole) tablet administered as a single oral dose (without chewing)=
- Treatment B = Ticagrelor 90 mg tablet crushed and suspended in water (test product)
- Treatment C = Dispersed ticagrelor 90 mg tablet suspended in water and administered through a nasogastric tube into the stomach (test product)=

There will be 3 treatment periods of 4 days each, with each period separated by a washout period of at least 7 days between doses. During each treatment period, the volunteer will stay at the study centre from the evening before administration of the investigational product (Day -1) until 48 hours (Day 3) after administration of the investigational product on Day 1. The follow-up procedures will be performed 5 to 10 days after the last dose in treatment period 3.

#### Target subject population

Healthy male and female volunteers aged 18 to 50 years (inclusive) who have a body mass index between 18 and 30 kg/m^2 (inclusive) and weigh at least 50 kg (110 pounds) and no more than 100 kg (220 lbs).

#### Investigational product, dosage and mode of administration

- Treatment A = Ticagrelor 90 mg (whole) tablet administered as a single oral dose (without chewing)
- Treatment B = Ticagrelor 90 mg tablet crushed and suspended in water (test product)
- Treatment C = Dispersed ticagrelor 90 mg tablet suspended in water and administered through a nasogastric tube into the stomach (test product)

#### **Duration of treatment**

The study will consist of screening 28 days prior to administration of the first dose; 3 treatment periods of 4 days each, with each period separated by a washout period of at least 7 days between doses; and a follow-up 5 to 10 days after the last dose. The total duration from enrolment of volunteers in the study to follow-up will be approximately 60 days.

#### **Outcome variables:**

• Pharmacokinetics

The following pharmacokinetic parameters will be calculated for ticagrelor and its metabolite AR-C124910XX in plasma:

- Observed maximum plasma concentration (Cmax)
- Time of maximum concentration  $(t_{max})$
- Area under plasma concentration-time curve from zero (pre-dose) to the last quantifiable concentration [AUC(0-t)]
- Area under plasma concentration-time curve from zero (pre-dose) to infinity (AUC)
- Apparent terminal half-life  $(t_{1/2})$

Additionally, metabolite to parent ratios (AR-C124910XX : ticagrelor) will be computed for  $C_{max}$ , AUC(0-t), and AUC.

• Safety

Adverse events, laboratory variables, vital signs, physical examination, and electrocardiogram (ECG).

#### **Statistical methods**

All safety and pharmacokinetic data recorded during the study will be listed and summarised as appropriate. Continuous variables will be summarised using descriptive statistics (n, mean, standard deviation, minimum, median, maximum) by treatment groups and by time points where applicable. Categorical variables will be summarised in frequency tables (frequency and proportion) by treatment group. Graphical presentations will be used as appropriate.

Ticagrelor and AR-C124910XX PK parameters AUC and  $C_{max}$  will be analysed using a mixed-effects model. The results will be presented as geometric least-squares means (95% CIs) and the ratios of geometric least-squares means (90% CIs). The treatment comparisons will be test (Treatments B or C) versus reference (Treatment A).

The safety, tolerability, adverse events will be coded using the Medical Dictionary for Regulatory Activities (MedDRA) for system organ class and preferred term. Adverse events will be summarised by Preferred Term and System Organ Class using MedDRA vocabulary by treatment and across all treatments. Medications will be classified according to the AstraZeneca Drug Dictionary. Tabulations and listings of data for vital signs, clinical laboratory tests, ECGs, and physical examination will be presented. For clinical laboratory

tests, listings of values for each volunteer will be presented with abnormal or out-of-range values flagged.

## LIST OF ABBREVIATIONS AND DEFINITION OF TERMS

The following abbreviations and special terms are used in this study Clinical Study Protocol (CSP).

Abbreviation or special term	Explanation
ACS	Acute coronary syndrome
ADP	Adenosine diphosphate
AE	Adverse event (see definition in Section $6.3.1$ )
ALP	Alkaline phophatase
ALT	Alanine aminotransferase
ANOVA	Analysis of variance
aPTT	Activated partial thromboplastin time
ASA	Acetylsalicylic acid
AST	Aspartate aminotransferase
AUC	Area under the plasma concentration-time curve
%AUC ex	Percent of area extrapolated for area under the plasma concentration-time curve from zero to infinity
AUC (0-t)	Area under the plasma concentration-time curve from zero to the last quantifiable concentration
В	Blood
BLQ	Below limit of quantitation
BMI	Body mass index
BP	Blood pressure
CAD	Coronary artery disease
CI	Confidence intervals
C max	Observed maximum plasma concentration
СРА	Clinical Pharmacology Alliance
СРТР	Cyclopentyltriazolopyrimidine
CSP	Clinical Study Protocol
CSR	Clinical Study Report
CV%	Co-efficient of variation
СҮР	Cytochrome P450
DAE	Discontinuation of investigational product due to adverse event

DNADeoxyribonucleic acidECGElectrocardiogrameCRFElectronic Case Report FormFDAFood and Drug Administration	
eCRF Electronic Case Report Form	
FDA Food and Drug Administration	
FSH Follicle-stimulating hormone	
GCP Good Clinical Practice	
GCV% Geometric coefficient of variation	
GMP Good Manufacturing Practice	
GRand AstraZeneca global randomisation syste	em
HBsAg Hepatitis B surface antigen	
HCV Hepatitis C virus	
HIV Human immunodeficiency virus	
IATA International Air Transport Association	
ICF Informed Consent Form	
ICH International Conference on Harmonisat	tion
IPA Inhibition of platelet aggregation	
$\lambda_z$ Apparent terminal rate constant	
LC-MS Liquid chromatography and mass spectr	cometry
LIMS Laboratory Information Management Sy	ystem
LLOQ Lower limit of quantification	
max Maximum	
MedDRA Medical Dictionary for Regulatory Activ	vities
MI Myocardial infarction	
min Minimum	
MTD Maximum tolerated dose	
NA Not applicable	
NB Nota bene (Latin for note well)	
ND Not determined	
NQ Non-quantifiable	
NSAIDs Non-steroidal anti-inflammatory drugs	
INR International normalised ratio	
NSTEMI Non-ST segment elevation myocardial i	infarction

Abbreviation or special term	Explanation
P2Y 12	A G protein-coupled purinergic receptor found mainly on the surface of blood platelet cells and is an important regulator in blood clotting
РК	Pharmacokinetics
PLATO	A study of platelet inhibition and patient outcomes (AstraZeneca Study D51305262)
РТ	Prothrombin time
QP	Qualified person
R&D	Research and Development
Rsq	Regression coefficient
S	Serum
SAE	Serious adverse event (see definition in Section 6.3.2).
SD	Standard deviation
SOC	System organ class
STEMI	ST segment elevation myocardial infarction
SUSARs	Suspected unexpected serious adverse reactions
$t_{1/2}$	Apparent terminal half-life
t max	Time of maximum plasma concentration
TT	Thrombin time
U	Urine
UA	Unstable angina
ULN	Upper limit of normal

## 1. INTRODUCTION

## 1.1 Background

Atherosclerosis is a progressive disease of the large conduit arteries. It is a worldwide public health concern, primarily due to the death and disability caused through its clinical manifestations as coronary (eg, unstable angina [UA] and myocardial infarction [MI]) and cerebral (eg, stroke and transient ischemic attack) thrombotic events. The term "acute coronary syndromes" (ACS) encompasses a range of clinical conditions that includes UA, non-ST segment elevation myocardial infarction (NSTEMI), and ST segment elevation myocardial infarction (STEMI). The process central to ACS is disruption or erosion of an atherosclerotic plaque, ultimately leading to the promotion of platelet aggregation and a thrombus.

Ticagrelor (BRILINTATM, BRILIQUETM) is a P2Y12 platelet inhibitor indicated to reduce the rate of thrombotic cardiovascular events in subjects with ACS. Ticagrelor has been shown to reduce the rate of a combined endpoint of cardiovascular death, MI or stroke compared to clopidogrel. The difference between treatments was driven by cardiovascular deaths and MIs with no difference in stroke. In subjects treated with percutaneous coronary intervention, it also reduces the rate of stent thrombosis.

BRILINTA $^{\text{TM}}$  was approved on 20 July 2011 to reduce the rate of thrombotic cardiovascular events in patients with ACS (UA, NSTEMI, or STEMI).

## **1.2** Summary of relevant preclinical and clinical information

Adenosine diphosphate (ADP) is one of the primary mediators of platelet aggregation, and inhibition of ADP mediated platelet aggregation by clopidogrel in combination with acetylsalicylic acid (ASA) has been shown to provide improved efficacy over ASA therapy alone in ACS, with a favourable bleeding profile. However, clopidogrel has a slow onset of action, irreversibly binds to its receptor resulting in a slow offset of effect, and often has incomplete and variable inhibition of platelet aggregation (IPA) from patient to patient.

Ticagrelor is an oral, reversible ADP receptor antagonist acting via the P2Y12 receptor, which has been developed for the prevention of thrombotic events in patients with ACS. The goal of the ticagrelor phase III programme was to demonstrate substantial improvements in clinical efficacy (ie, clinical thrombotic event reduction) with an acceptable safety profile compared with currently available antiplatelet therapies (ie, ASA and clopidogrel). Most patients took concomitant ASA with ticagrelor. Inhibition of platelet aggregation mediated by ticagrelor increases with increasing plasma concentrations of ticagrelor and its active metabolite, AR-C124910XX, until almost complete inhibition is obtained. Ticagrelor has a more rapid onset, higher and less variable inter-patient IPA, and faster offset compared to clinical doses of clopidogrel.

The focus of the clinical pharmacology program for ticagrelor, has been to examine the exposure-response relationship, investigate safety, and characterise drug interactions. The

pharmacokinetics (PK) of ticagrelor, as well as the metabolism of the compound, has been characterised in healthy subjects and patients with coronary heart disease. The dose range of ticagrelor administered during these studies was 0.1 to 1260 mg, and 900 mg was established as the maximum tolerated dose (MTD) in healthy subjects.

## **1.3** Rationale for conducting this study

Alternative ways of administering a tablet are useful to help patients who, for different reasons, have difficulties with swallowing a whole tablet. Administration of dispersed tablets suspended in water is a common way of administering drugs to these patients. A useful method in patients whose condition prevents swallowing is administration of dispersed tablets through nasogastric tubes.

The purpose of this study is to evaluate the bioavailability of two alternative methods of administration of crushed ticagrelor tablets compared to whole ticagrelor tablets in healthy volunteers. The results of this study will define the alternative ways of administration of ticagrelor tablets.

## 1.4 Benefit/risk and ethical assessment

There are no direct benefits for the volunteers participating in this study. However, study related health assessments are provided at no cost.

As a consequence of the pharmacological properties of ticagrelor, there is an increased risk for bleeding. However, in this study as only a single dose is administered in each treatment period (within the therapeutic dose range) with adequate washout between the treatment periods, the risk for bleeding has been minimised. Moreover the inclusion and exclusion criteria have considered the contraindication and warning suggested by regulatory approved prescribing information.

Ticagrelor, like other inhibitors of platelet aggregation, increases the risk of bleeding. Reported events in previous Phase II and Phase III studies have included bleeding in areas considered to be clinically important such as the lung, brain, eye, and joints. In previous studies in healthy volunteers, adverse events (AEs) associated with bleeding were infrequent and were generally considered to be mild. In this study, necessary measures will be taken to minimise this risk of bleeding by excluding volunteers at high risk of bleeding such as volunteers with history of haemophilia, von Willebrand's disease, lupus anticoagulant, or other diseases/syndromes that can either alter or increase the propensity for bleeding. Also volunteers with a history of a clinically significant nontraumatic bleed or clinically significant bleeding risk, as judged by the Investigator, will be excluded.

The risk of ticagrelor exposure to volunteers in this study is expected to be equivalent to the safety profile in volunteers observed in previous Phase I studies where similar doses have been administered. The most common AEs, with an incidence of at least 2%, reported to date in the Phase I studies with at least 3 days of ticagrelor dosing include headache, somnolence, dizziness, epistaxis, nausea, abdominal pain, back pain, dyspnoea, ecchymosis, lethargy,

pharyngolaryngeal pain, blurred vision, postural dizziness, pollakiuria (frequent urination), and increased tendency for bruising.

Ticagrelor is well tolerated in single doses up to 900 mg and multiple doses up to 600 mg per day. The highest single dose studied was 1260 mg where adverse gastrointestinal effects limited tolerability and therefore established 900 mg as the maximum tolerated dose.

Dyspnoea was observed in patients with coronary artery disease (CAD) but rarely in healthy subjects. Ticagrelor does not appear to affect respiratory parameters in elderly subjects, patients with asthma or chronic obstructive pulmonary disease, and stable CAD patients.

When ticagrelor was administered orally to healthy subjects for 5 days under controlled conditions of diet, activity, and fluid intake, serum uric acid levels increased approximately by 10%, with no extreme individual elevations, and returned to baseline within 60 hours of discontinuing ticagrelor.

Ticagrelor (single 900 mg dose) had no cardiac ventricular repolarisation effect during the first 24 hours after administration compared with placebo as assessed by QT interval. In the PLATO study, more patients had ventricular pauses >3 seconds with ticagrelor than with clopidogrel, however, there were no adverse clinical consequences associated with this imbalance (including pacemaker insertions) in this population of patients.

For further relevant pre-clinical and clinical data see the current Investigator's Brochure.

In addition, this study requires application of a nasogastric tube and nose bleeding is not an uncommon effect with nasogastric tube insertion, therefore nasogastric tube will be applied by someone with experience. AstraZeneca will immediately notify the Investigator of important safety data that becomes available during the study.

## 2. STUDY OBJECTIVES

## 2.1 Primary objective

To evaluate the bioavailability of the crushed ticagrelor tablets when administered orally or through nasogastric tubes as aqueous solution, compared to whole ticagrelor tablets given orally by assessment of the area under the plasma concentration-time curve (AUC) and maximum plasma concentration ( $C_{max}$ ) for both ticagrelor and AR-C124910XX, the active metabolite of ticagrelor.

## 2.2 Secondary objectives

To examine the safety and tolerability of ticagrelor when administrated as dispersed tablets orally, dispersed tablets via nasogastric tube and as whole tablet orally by assessment of AEs, safety laboratory variables, physical examination, electrocardiogram (ECG) and vital signs.

## 3. STUDY PLAN AND PROCEDURES

This CSP has been subject to a peer review according to AstraZeneca Standard Operating Procedures.

## 3.1 Overall study design and flow chart

[figure not shown]
This study is a single-centre, open-label, randomised, 3-period, 3-treatment crossover study in which healthy volunteers will receive single doses of ticagrelor in three different ways (treatment A, B, and C). The dose will be administrated as

- Treatment A = Ticagrelor 90 mg (whole) tablet administered as a single oral dose
- Treatment B = Ticagrelor 90 mg tablet crushed and suspended in water (test product)
- Treatment C = Dispersed ticagrelor 90 mg tablet suspended in water and administered through a nasogastric tube into the stomach (test product)

Up to 36 healthy volunteers, males and females between the ages of 18 and 50 years (inclusive) will be randomised to ensure that at least 30 volunteers are evaluable at the end of the study.

There will be 3 treatment periods of 4 days each, with each period separated by a washout period of at least 7 days between doses. During each treatment period, the volunteer will stay at the study centre from the evening before administration of the investigational product (Day -1) until 48 hours (Day 3) after administration of the investigational product on Day 1. The follow-up procedures will be performed 5 to 10 days after the last dose in treatment period 3. A study flow chart is provided in Figure 1 and the study plan is presented in Table 1

#### Figure 1 Study flow chart

a Up to 28 days before first study day

b Administration of the investigational product according to randomisation; either Treatment A, Treatment B or Treatment C.

c at least 7 days

Treatment A: Ticagrelor 90 mg (whole) tablet administered as a single oral dose

Treatment B: Ticagrelor 90 mg tablet crushed and suspended in water

Treatment C: Dispersed ticagrelor 90 mg tablet suspended in water and administered through a nasogastric tube into the stomach

#### Table 1

Study plan

	Visit 1		Vi	sit 2, 3, 4		Visit 5
Assessment	Screening visit	Day -1	Day 1	Day 2	Day 3	Follow-up
	Up to 28 days before first study day	Day before treatment	Treatment day	24 hours after treatment	48 hours after treatment	(5 to 10 days after last dose)
Informed consent	X					
Demographics	X					
Inclusion and exclusion criteria	X	X a				
Medical and surgical history	X	X b				
Complete physical examination d	Х					Х
Brief physical examination		X c			Х	
12-Lead electrocardiogram	Х				Х	Х
Vital signs (blood pressure and pulse rate)	Х	X e	Xe	Xe	Х	Х
Safety laboratory assessments	Х	X c,f			Х	Х
PT and aPTT		X			Х	
Assessment of FSH g	X					
Virology screen h	Х					
Pregnancy test i	X	X c				Х
Drugs of abuse screen	X	X c				
Urine alcohol test	Х	X c				
Randomisation j			X			
Ticagrelor dose administration			X			
Ticagrelor pharmacokinetic sampling k			X	Х	Х	

	Visit 1 Visit 2			it 2, 3, 4		Visit 5
Assessment	Screening visit	Day -1	Day 1	Day 2	Day 3	Follow-up
	Up to 28 days before first study day	Day before treatment	Treatment day	24 hours after treatment	48 hours after treatment	(5 to 10 days after last dose)
Recording of concomitant medication		Х	X	Х	Х	Х
Adverse event monitoring 	X	Х	Х	Х	Х	Х
Confinement to study centre		X m	X m	X m	X m	
Insertion and removal of nasogastric tube			X n			

The study plan is applicable to all treatment periods.

FSH: Follicle-stimulating hormone; aPTT: Activated partial thromboplastin time; PT: Prothrombin time; TT: Thrombin time

a Inclusion and exclusion criteria will be checked within 24 hours prior to administration of the investigational product during treatment period 1 only.

- b Updating of medical/surgical history to be done on Day -1 of treatment period 1 only.
- c To be performed within 24 hours prior to administration of the investigational product in each treatment period.
- d Complete physical examination at screening and follow-up. Height (centimetres) and weight kilograms) and BMI will be measured at screening only
- e Vital signs will be recorded at screening, pre-dose, 1 hour, 3, 6, 12 and 24 hours post-dose, Day 3 for all treatment periods and follow-up visit
- f Safety laboratory assessments should be analysed and checked before randomisation.
- g In self declared post-menopausal female volunteers only
- h Includes hepatitis B, hepatitis C, and human immunodeficiency virus (HIV) screens.
-  For female volunteers only; urine pregnancy test will be performed at screening, Day -1 (all treatment periods) and at follow-up.
- j Will occur on Day 1 of treatment period 1.
- k Pharmacokinetic blood sampling will be done at pre-dose, 0.5, 1, 2, 3, 4, 6, 8, 10, 12, 16, 24, 36 and 48 hours post-dose for determination of ticagrelor and AR-C124910XX concentrations in plasma.
-  Serious adverse events (SAEs) will be collected from the time of obtaining informed consent through to the follow-up visit. All other AEs will be collected from the time of the first dose on Day 1 (treatment period 1) through to the follow-up visit.
- m Discharge from the study centre will be after the PK sampling at 48 hours post-dose is obtained.
- n According to randomised treatment.

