#### 6.3.3 Recording of adverse events

#### Time period for collection of adverse events

Adverse events will be collected from the time of signature of informed consent throughout the treatment period and including the follow-up period.

All SAEs will be recorded from the time of informed consent.

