# 11. EVALUATION AND CALCULATION OF VARIABLES

# **11.1** Calculation or derivation of safety variable(s)

All AEs will be collected for each volunteer from the time when informed consent is obtained until the follow-up visit.

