#### 12.2.2 Safety and tolerability

The following safety clinical assessments will be done: AEs, vital signs, physical exams, clinical chemistry and haematology, and ECGs. All safety data (scheduled and unscheduled) will be presented in the data listings.

All safety data (scheduled and unscheduled) will be presented in the data listings. Continuous variables will be summarised using descriptive statistics (n, mean, SD, min, median, max) by treatment at each scheduled time and for the corresponding change from baseline where applicable. Categorical variables will be summarised in frequency tables (frequency and proportion) by treatment group and by scheduled time where applicable. Safety variables (eg, clinical laboratory values and vital signs) will be reported to the same precision as the source data. Derived variables will be reported using similar precision to those from which they were derived (eg, QTc derived from QT interval).

Extra measurements (such as unscheduled or repeat assessments) will not be included in the descriptive. All AEs, ECG outliers, and clinical laboratory outliers that occur following the first administration of the investigational product will be included in the tabulations of AEs and outlier events, including episodes that occur at unscheduled evaluations.

All available data from volunteers in the safety analysis set will be included in the safety analyses. No adjustment or imputation will be utilised for missing values or for volunteers who withdraw prior to completing the study, neither will analyses be restricted to volunteers with complete data.

All AEs will be collected for each volunteer from the time when informed consent is obtained until the follow-up visit. Adverse events that occur before dosing will be reported separately. Adverse events will be summarised by Preferred Term and System Organ Class using Medical Dictionary for Regulatory Activities (MedDRA) vocabulary (Version 12.0 or higher) by treatment and across all treatments, as appropriate. Furthermore, listings of SAEs and AEs that lead to withdrawal will be presented and the number of volunteers who have any AEs, SAEs, AEs that lead to withdrawal, and AEs with severe intensity will be summarised.

For clinical laboratory tests, listings of values for each volunteer will be presented with abnormal or out-of-range values flagged. Clinical laboratory data will be reported in Système International units in the CSR.

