#### **Adverse Events**

All AEs will be collected for each volunteer from the time when informed consent is obtained until the follow-up visit. Adverse events that occur before administration of the investigational product will be reported separately.

Adverse events will be summarised by Preferred Term and System Organ Class (SOC) using MedDRA vocabulary (Version 12.0 or higher) by treatment and across all treatments. Furthermore, listings of SAEs and AEs that lead to withdrawal will be made and the number of volunteers who have any AEs, SAEs, AEs that lead to withdrawal, and AEs with severe intensity will be summarised.

All AEs occurring at any time during the study will be listed. All summary tables of AE data will include all AEs starting or worsening after administration of the investigational product. Overall summaries of AEs will be provided at both the volunteer level and the event level, detailing the number of AEs, SAEs, discontinuations due to AEs and other significant AEs by treatment. Adverse events will be summarised by treatment by SOC and preferred term assigned to the event using the MedDRA vocabulary. In volunteer level summaries, a volunteer will only be counted once in each SOC or preferred term. Adverse events will also be summarised by treatment by maximum intensity and by investigator's causality assessment. In addition, separate listings for all SAEs, OAEs, deaths and discontinuations due to AEs will be presented.

Any AEs determined to be of interest or occurring frequently may be summarised separately using the same methodology as described above.

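### The Table 1 footnote starts non-serious AE collection at the first dose, while sections 6.2.1, 6.3.3, 11.1 and 12.2.2 start it at consent; the two must be reconciled before enrolment

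*Protocol*

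**What the plan says.** The protocol sets the start of adverse event (AE) collection in several places.

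- **Table 1, AE footnote (section 3.1).** It separates two classes of event. For serious events: "Serious adverse events (SAEs) will be collected from the time of obtaining informed consent through to the follow-up visit". For the rest: "All other AEs will be collected from the time of the first dose on Day 1 (treatment period 1) through to the follow-up visit".
- **Table 1, AE row.** The row labelled "Adverse event monitoring" is marked at screening, Day -1, Days 1 to 3 and follow-up, and carries that footnote.
- **Section 6.2.1.** The screening procedures include recording both AEs and SAEs, if there are any.
- **Section 6.3.3.** "Adverse events will be collected from the time of signature of informed consent throughout the treatment period and including the follow-up period". A separate sentence then gives consent as the start for SAEs.
- **Section 11.1, repeated in section 12.2.2.** "All AEs will be collected for each volunteer from the time when informed consent is obtained until the follow-up visit".
- **Section 12.2.2, planned output.** "Adverse events that occur before dosing will be reported separately"; under its Adverse Events heading, "Adverse events that occur before administration of the investigational product will be reported separately" and "All AEs occurring at any time during the study will be listed".

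**The concern.** For a non-serious event between consent and the first dose, the footnote says not to collect it and the other sections say to collect it. Both cannot be followed, and no sentence gives an order of precedence.

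The footnote could well be the rule applied in practice, because section 6 sends staff to Table 1 for the study assessments. The analysis section, by contrast, is written as if pre-dose non-serious events will be in the database.

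At stake are the completeness of the planned pre-dose AE report and listing, and the capture of events caused by tube insertion before the first dose. Safety and tolerability of the nasogastric route is part of the secondary objective. Non-serious events that were never recorded cannot be reliably recovered later.

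**Working it through.** The protocol gives no figure to reproduce here. The check is a side-by-side reading plus one count.

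**Step 1. Start of collection in each place**

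| Place | Non-serious AEs start at | SAEs start at |
|---|---|---|
| Table 1 footnote | first dose, period 1 | consent |
| Section 6.2.1 | screening | screening |
| Section 6.3.3 | consent | consent |
| Section 11.1 | consent | consent |
| Section 12.2.2 | consent | consent |

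The SAE column is compatible throughout. The non-serious column is not.

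**Step 2. Can the wording be harmonised?** The footnote contrasts SAEs with all other AEs, so its later start is deliberate for non-serious events. Section 6.3.3 treats SAEs in a sentence of their own, so its general sentence cannot be read as meaning SAEs only. The marks in Table 1 at screening and Day -1 do not settle the matter, because under the footnote they can stand for SAE monitoring alone. Section 6.3.1 also allows an AE to occur before any investigational product has been given.

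**Step 3. Effect on the planned output if the footnote is followed.** Events before the first dose that reach the database are SAEs only. The separate pre-dose report can then contain nothing else, and the listing of all AEs at any time is incomplete for the period from consent to first dose. An empty pre-dose report has two explanations that cannot be told apart.

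**Step 4. Tube insertion.** Section 1.4 describes nose bleeding as a not uncommon effect of inserting the tube. Table 1 places insertion on Day 1, and insertion must precede a dose given through the tube. Section 5.2.1 allocates volunteers equally to the 6 sequences of a Williams design. With three treatments, each treatment comes first in 2 of the 6.

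Volunteers with insertion before their first study dose = 36 × 2/6 = 12.

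For these volunteers, a non-serious event between insertion and first dose lies outside the footnote's window. For the other 36 − 12 = 24, who receive C in period 2 or 3, the same event follows the first study dose and lies inside it. Twelve counts volunteers exposed to the gap. The protocol gives no rate of insertion events, so the number of events cannot be derived.

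**Step 5. Does the gap reach the AE summary tables?** Section 12.2.2 limits those tables to events that begin or get worse once drug has been given. Non-serious events confined to the time before the first dose would not enter them under either rule.

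**The case against.** The strongest reply is that the plan read as a whole points to consent. Section 6.3 makes the investigator responsible for seeing that all staff know its contents, which include the consent-onward rule, and section 6.2.1 is a site-facing list that records AEs at screening. This stands: loss of data is a risk, not the expected result. It does not remove the contradiction, since Table 1 is the place to which staff are directed for assessments.

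The second reply is that little depends on it. The primary objective is pharmacokinetic, SAEs are covered under both rules, the safety set requires a dose and post-dose data, and the AE summary tables are post-dose. This also stands, and it limits the severity.

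A reader might go further and infer that worsening after dosing cannot be judged at all without pre-dose AE records. The protocol does not support that. Medical history is updated on Day -1 of period 1, a brief examination and safety laboratory tests are done before dosing, and vital signs are taken pre-dose. These give a partial baseline. They do not cover every symptom, in particular one arising on Day 1 before dosing.

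A reader might also take 12 as a number of lost events, or the screening window of up to 28 days as 28 days of lost observation. Neither follows. The 12 are volunteers exposed. The 28 days are a maximum, most of it spent outside the study centre, since confinement begins on Day -1.

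**Conclusion.** The inconsistency is real, lies in current text and concerns what the site records, so it is not a detail that a statistical analysis plan would normally settle. Its severity is moderate.

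If the footnote is followed, the pre-dose AE report is restricted to SAEs and cannot be interpreted when empty. Non-serious insertion events before the first dose are missed in about 12 of 36 volunteers exposed, with an unknown event count. That figure assumes all 36 are randomised, allocation is balanced and every volunteer who starts with C has the tube inserted before dosing.

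The primary pharmacokinetic analysis, SAE collection and most post-dose AE summaries are not affected. The protocol does not support a conclusion that the by-treatment safety comparison as a whole is compromised.

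**What to change.** Before enrolment, replace the two-part AE footnote to Table 1 with a single statement that all AEs, serious and non-serious, are collected from signature of informed consent to the follow-up visit. This matches sections 6.2.1, 6.3.3, 11.1 and 12.2.2, which need no change.

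The cost is one footnote. No visit or assessment is added, because the AE row is already marked at screening and Day -1.

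The change restores capture only. Under the Adverse Events part of section 12.2.2, an insertion event before the first dose would still be reported separately as pre-dose and would stay out of the post-dose summary tables unless it worsened. The difference between period 1 and later periods could therefore persist in those tables, and the pre-dose report should be read alongside them when tolerability of Treatment C is described.
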